APPENDIX A INVESTIGATOR INITIATED PROTOCOL TEMPLATE

Additional Details Pertaining to Study Design for Clinical Trials

1. For a clinical trial (e.g. a Phase I, II or III study), the use of the intervention must be fully described e.g., the treatment regimen for use of drugs, placebo, medical device etc. Also include plans for receipt of test article, storage, dispensing and reconciliation.

Participants will be given a one-week supply of preferred flavor little cigars/cigarillos (LCCs) and a one-week supply of plain (unflavored) LCCs (order randomized). We will dispense a brand of LCCs that are already on the market and popular, such as Black and Milds. Every participant will be given the same brand and presented with the same flavor choices. The products that we will dispense are not new nor experimental. Moreover, it should be noted that the participants will be regular smokers of LCCs in order to qualify for the study.

We will order our supply of LCCs from an online vendor and store them in a secured location in the CRC. Only trained study personnel—the PI ([name]), CRC research assistants, or UConn undergraduate student research assistants—will dispense the products at Visits 2 and 3. Study personnel will use the participants’ normal usage patterns of LCCs to determine how many to dispense. At the end of each one-week period, participants will return unused LCCs to the study personnel. Unopened products can be used for future participants.

2. Provide a description of known adverse events due to the intervention and the plan to deal with such adverse events (e.g. does reduction, removal of device, removal from trial.):

Participation in the study should not pose additional risks to participants. To be eligible to participate in the study, participants must already be a current, regular dual user of LCCs. That is, they are already exposing themselves to the harms associated with LCC use. Therefore, the proposed study poses low risk of harm to participants, and we expect that SAEs will be rare and not related to study participation.

We will collect all respiratory and other AEs on a log (see attached) and enter them into a tracking database. Each AE will be graded (mild, moderate or severe). SAEs will be also noted. Additionally, we will note probable cause (unrelated, possibly related, or definitely related to the study). AEs and SAEs, even those clearly unrelated to the study such as accident or illness, will also be reported to [name], and to either [name] or [name]. Any concerning events that could be related will be reviewed on an ongoing basis at study meetings. Drs. [name] and [name] or [name] will determine how to proceed in consultation with Drs. [name] and [name] as needed.

Participants who experience any of the following will be said to have experienced an SAE, as defined by the FDA:

- Death
- Suicide or homicide attempt
- Persistent, serious suicidal or homicidal ideation, with intent and plan

- **Congenital Abnormality or permanent disability**
- **Life-threatening events**
- **Overnight hospitalization (excluding planned surgeries or other planned procedures)**

Any participant who experiences an AE or SAE will be assessed for causality, and referred to treatment if necessary. Any participant who experiences an SAE will be advised regarding options to continue or terminate participation in the study. All AEs will be reported to the IRB on an annual basis. All SAEs will be reported to the IRB within the required time limits.

3. Describe circumstances that may lead to a subject being removed from the trial by the PI, e.g. due to failure to follow study procedures, and the process for doing so:

Participants who fail to show up to their appointments five times in a row will be removed from the study. Study staff will notify them via email or phone.

4. Describe any stopping rules for the study: **In the event that several SAEs are recorded in a short space of time (i.e., more than 6 in one month), or if a pattern of SAEs becomes apparent (e.g., one treatment condition results in many more SAEs than the other condition), [name] and her mentors on the study Drs. [name], [name], [name], and [name] review the data and make one of the following determinations: 1) continue recruitment unchanged; 2) continue after a protocol amendment; or 3) stop recruiting pending further investigation.**
5. Additional Comments by PI: **None**

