- **Study design:** The study will employ a prospective, randomized cross-over design with 125 non-treatment-seeking young adult (18-34) dual users of cigarettes and LCCs. Using the original CPT and the CPT modified for LCCs, we will assess demand for cigarettes as cigarette price increases, demand for flavored and unflavored LCCs as prices for these products increase, and demand for flavored and unflavored LCCs as *cigarette* price increases across two study visits. Prior to each visit, participants will receive (in random order) their preferred flavor and unflavored LCCs to use at home to validate their responses on the CPT. Study visits will take place 7 to 10 days apart. This strategy has been used in our previous study of e-cigarettes and shown to be a sufficient time period to examine the impact of flavors on likeability of the product [64]. See **Figure 2**.

[figure not shown]

Figure 2. Randomized crossover study design

- **Sample size and justification:** We will enroll 125 non-treatment-seeking young adults (18-34) who are regular dual users of cigarettes and LCCs (see inclusion criteria for definition). Sample size calculation: No studies to date have investigated the main outcome for the proposed study: demand elasticity and intensity for flavored and unflavored LCCs, and cross-price elasticity of flavored and unflavored LCCs for cigarettes [65-68]. Published cross-price elasticities of LCCs for cigarettes range from 2.73 for little cigar sales [67] to 174.5 for cigarillo sales in exclusive, daily cigarette smokers [65]. Therefore, the sample size was calculated in G*Power 3 (94) using the standard medium effect size ($d=0.5$) for two independent means [69], in order to capture statistically significant differences by sex. With a sample size of 102, we can detect an effect size of 0.5 with 80% power and $\alpha=0.10$. In [name] pilot study with dual users [70], the attrition rate was 18%. Therefore, the final sample size of 125 participants will account for attrition.

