- **Explain on what basis it is reasonable to assume that the sample size will be obtained:** Recruitment will take place over 18 months, requiring enrollment of about nine subjects per month. We will recruit from the community using flyers, subject referral, newspaper ads, radio ads, bus ads, and online sources like Craigslist.com. In [name] pilot study with African American young adult dual users (18-29), 63 participants were recruited in four months (~16 participants enrolled per month) using primarily Craigslist and subject referral (unpublished). Therefore, the proposed recruitment timeline is feasible.
- **Method(s) of data analysis:** Descriptive statistics including means (SDs) and frequencies (percentages) will be reported to describe demographic characteristics and smoking history.

From the CPTs, demand curves for LCCs (own brand, preferred flavor, and unflavored) and cigarettes will be graphically plotted, and consumption as a function of cost will be calculated using the Exponential Model of Demand [71, 72]. From the demand curves, the following indices will be calculated using standard equations [55, 72]: (a) breakpoint, (b) intensity, (c) elasticity and cross-price elasticity, (d) O_{\max} , and (e) P_{\max} . For Aims 1 and 2, the demand indices for own brand of LCCs, preferred flavor LCCs, unflavored LCCs, and cigarettes will be compared. In addition, the cross-price elasticity will be calculated using an extension of the exponential model of demand to determine how demand for LCCs (own brand, preferred flavor, and unflavored) changes as a function of cigarette price [73], adjusting for age, gender, race, and menthol status. Survey-based measures of LCC impressions, risk perceptions, and dependence will be calculated, compared by product using Analysis of Variance (ANOVA) tests, and correlations with demand indices will be examined. For Aim 3, the models will be stratified by gender to compare demand indices in women and men. In post-hoc analysis the demand indices will be stratified by race/ethnicity to detect any differences in the addictive potential of the products.

Subject Characteristics:

- Age: 18-34 years
- Ethnicity: All are eligible
- Gender: approximately 50% women and 50% men
- Vulnerable Populations: No special vulnerable populations (such as fetuses, neonates, pregnant women, children, prisoners, and institutionalized individuals) will be involved.
- Other characteristics: None
- Inclusion Criteria:

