- **All Recruitment Methods and Materials:** Participants will be recruited from the community using flyers, subject referral, newspaper ads, bus ads, radio ads, and online sources. Flyers (see attached) will be distributed at colleges, community centers, bars, and music venues in the communities in and near Farmington, Hartford, and Storrs. We will also run ads in the local buses and on local radio stations (see attached). Each radio ad runs for about 2 weeks, and each bus ad for about 4 weeks. We will also run ads in local newspapers, like the Yankee Flyer (see attached). Online sources, such as Facebook, Craigslist, and Google Ads, will also be used (see attached), and work especially well for recruiting young adults [81, 82]. We will also use these online ads for the UCHC Broadcast email. Lastly, we will ask participants to refer their friends to the study, and give them cards to distribute (see attached). All recruitment materials contain the study's phone number, website address to complete the screener, Google voice number to text, and email address. For participants who call, research staff will complete the screener over the phone. In addition to phone, interested individuals may also contact the study staff in response to recruitment materials by email or text. Study staff will contact individuals by phone, voice, and/or text to determine interest in participating in the study and, if interested, to refer them to the online screener or set up a phone call for screening. Recruitment will take place over 13 months, requiring enrollment of about 10 subjects per month. In [name] pilot study with young adult dual users, 63 participants were recruited in four months (~16 participants per month) using primarily Craigslist and subject referral. Therefore, the recruitment timeline is feasible. All recruitment procedures will be conducted by the PI ([name]), trained CRC research assistants, or trained UConn undergraduate student research assistants. Google voice will be used for texting only, and used from a secure device. It has been approved by IT security. A uhc email address has been obtained for the study, and will only be used from a secure device.

- Participants may receive reminder phone calls, text messages, and/or emails about upcoming appointments.

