The risks entailed in this study are considered reasonable and minimal because the source population (from which the study sample will draw) are individuals who are currently using both cigarettes and LCCs and have no interest in quitting. There will be an additional burden of time to complete the research procedures, but we will take every effort to streamline the assessments. There are no direct benefits to subjects for participation. We believe that the small risks of the study are outweighed by the potential benefits of understanding the addictive potential of LCCs and how that addiction changes when flavor is eliminated. We expect that there will be societal benefits in understanding the addictive potential of flavored vs. unflavored LCCs in young adult dual users, which will be useful for cessation programs and regulatory purposes.

D. Importance of Knowledge to be Gained

Smoking is one of the leading health problems in the U.S. The burden of multiple tobacco product and LCC use is growing, particularly in young adults. Our understanding of the addictive potential of LCCs, and the moderating effects of flavor and sex, is limited at this time. By providing information about their addictive potential, we expect to inform cessation efforts targeting young adult dual users and regulatory decision-making on LCCs for prevention and cessation.

DATA AND SAFETY MONITORING PLAN

[name] will assume primary responsibility for safety of this study, executing the data and safety monitoring plan (DSMP), and complying with reporting requirements, under the mentorship of Drs. [name], and [name]. Because the study is low-risk and single-site, there will not be a Data and Safety Monitoring Board. [name] will meet with the study personnel on a weekly basis, and will be available at any time to identify and solve problems in the study's implementation, and provide advice on any adverse events experienced by participants during the study. The research assistant will be responsible for the monitoring of participants and will report to [name] as needed.

A. Safety Monitoring

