The proposed study poses low risk of harm to participants; therefore, we expect that SAEs will be rare and not related to study participation. We will collect all respiratory and other AEs on log forms (see attached) and in a tracking database. Each AE will be graded (mild, moderate or severe). SAEs will be also noted. Additionally, we will note probable cause (unrelated, possibly related, or definitely related to the study). AEs and SAEs, even those clearly unrelated to the study such as accident or illness, will also be reported to [name] and either Drs. [name], or [name] (who are MDs). Any concerning events that could be related will be reviewed on an ongoing basis at study meetings. [name] and either Drs. [name], or [name] will determine how to proceed in consultation with Drs. [name] and [name] as needed.

Participants who experience any of the following will be said to have experienced an SAE, as defined by the FDA:

- Death
- Suicide or homicide attempt
- Persistent, serious suicidal or homicidal ideation, with intent and plan
- Congenital Abnormality or permanent disability
- Life-threatening events
- Overnight hospitalization (excluding planned surgeries or other planned procedures)

Any participant who experiences an AE or SAE will be assessed for causality, and referred to treatment if necessary. Any participant who experiences an SAE will be advised regarding options to continue or terminate participation in the study. All AEs will be reported to the IRB on an annual basis. All SAEs will be reported to the IRB of record within the required time limits.

B. Data Monitoring

[name] will assume primary responsibility for data accuracy and protocol compliance. Data will be collected securely electronically and double-checked by research staff. Audits of randomly selected participant files will be conducted quarterly to check on accuracy of data entry and protocol adherence. Adherence to protocols will also be ensured by ongoing supervision by [name], who will report regularly to Drs [name], and [name] in their regularly scheduled mentorship meetings. Protocol deviations as a result of staff error will be reported to the IRB with a protocol deviation report form. The protocol deviation report will outline the root cause of the problem and establish a plan of

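### The only numeric safety trigger, more than 6 SAEs in one month, is set too high to operate in a study of this size, and no listed outcome is an interim hold for people already enrolled

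*Combined protocol and SAP*

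**What the plan says.** Appendix A, item 4 (stopping rules) gives two ways into a review by the investigator and mentors. The first is a count: "In the event that several SAEs are recorded in a short space of time (i.e., more than 6 in one month". The second is an apparent pattern of SAEs, for which the example is that "one treatment condition results in many more SAEs than the other condition"; no number is attached. The review must end in one of three determinations: "1) continue recruitment unchanged; 2) continue after a protocol amendment; or 3) stop recruiting pending further investigation".

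The Data and Safety Monitoring Plan says: "Because the study is low-risk and single-site, there will not be a Data and Safety Monitoring Board". Its Safety Monitoring section states that "we expect that SAEs will be rare and not related to study participation". That section and Appendix A, item 2 also provide for the following:
- Events are graded, and relatedness to the study is recorded.
- SAEs, including unrelated ones, go to the study lead and a physician, and to the IRB within required limits.
- Possibly related events of concern are discussed at study meetings, after which the lead and a physician decide what to do next.
- A participant with an SAE is advised on whether to continue.

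Section B2 lets anyone stop using study LCCs at any time.

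**The concern.** A count trigger is useful only if a serious excess of events would reach it. Here at least seven SAEs must fall within one month, in a study that enrols seven to ten people a month and follows each for two to three weeks. SAEs are defined as deaths, life-threatening events, overnight hospitalizations and the like. The study could see far more of these than it expects without meeting the one number it has written down.

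The second gap is what a review can order. Stopping recruitment does not affect people already enrolled: a participant in Week 1 would still be given the other product at Visit 2. An amendment could change dispensing, but only once it is in force, and with 14 to 20 days on product most enrolled participants could finish before then. What is at stake is participant protection. The estimates and tests are not affected.

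**Working it through.** **Inputs.**
- Enrolment: 125. This reproduces from the plan's sample-size paragraph: 102 / (1 - 0.18) = 124.4, rounded up to 125.
- Accrual: the Study Design section says "Recruitment will take place over 18 months, requiring enrollment of about nine subjects per month", but 125/18 = 6.9 per month (nine a month for 18 months would be 162). The recruitment-methods section says "Recruitment will take place over 13 months, requiring enrollment of about 10 subjects per month"; 125/13 = 9.6. I use 6.9 to 10 per month, which spans both.
- Time on product: "Study visits will take place 7 to 10 days apart", twice, so 14 to 20 days.
- Trigger: more than 6, so at least 7.
- SAE rate: not given. It is scanned below as an assumption.

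**People on study at some point in a month** = rate x (30.4 + days) / 30.4.
- Slow: 6.9 x 44.4/30.4 = 10.1, and 7/10.1 = 69%.
- Fast: 10 x 50.4/30.4 = 16.6, and 7/16.6 = 42%.

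**Rate needed for an even chance in a given month.** A Poisson count has P(7 or more) = 0.5 at a mean of 6.67. That is 6.67/10 = 0.67 to 6.67/6.94 = 0.96 SAEs per enrolled participant.

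**Simple Poisson check at 0.10 SAEs per participant.** The monthly mean is 0.69 to 1.0. P(7 or more) in a given month is 0.001% to 0.008%, and at most about 0.1% over the whole of recruitment.

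**Simulation of the whole study.** Entries are uniform over 18 months (14 days each) or 12.5 months (20 days each). SAEs per participant are Poisson with mean r, placed uniformly over time on study. Repeat events in one person are allowed and fall close together, which helps the trigger. The ranges run from slow to fast accrual.

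| Assumed r | SAEs expected (125 x r) | Ever 7+ in a calendar month | Ever 7+ in a rolling 30 days | Ever 3+ in a rolling 30 days |
|---|---|---|---|---|
| 1% | 1.25 | - | - | 0.27-0.56% |
| 2% | 2.5 | - | - | 2.0-3.8% |
| 5% | 6.25 | 0-0.01% | 0.01-0.03% | 23.6-34.0% |
| 10% | 12.5 | 0.05-0.18% | 0.32-0.92% | 74.8-86.8% |
| 20% | 25 | 2.9-8.8% | 10.1-25.8% | - |

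**Faster accrual.** At the pilot pace of 16 per month, 16 x 44.4/30.4 = 23.4 to 16 x 50.4/30.4 = 26.5 people pass through in a month, so seven is 26-30% of them. The written count is then ever met with probability 1.4-5.3% at r = 10% and 34-65% at r = 20%.

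**The case against.** The strongest reply is that the count is only a backup. Any SAE reaches the lead and a physician, meetings are weekly, and those two roles can decide how to respond to a concerning event without any count and without being confined to item 4's three outcomes. That authority could include holding product. This stands, so a reader should not infer that review depends entirely on the pattern clause. It also means that the relatedness half of the proposed trigger largely formalizes existing practice.

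A reader might also infer that the pattern clause is nearly empty because few people hold each product at one time. The text does not support that. A difference by condition is only an example, and a pattern can build up over the whole study, in which participants are due to receive both products.

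A reader might say that seven events cannot occur because fewer than seven people are usually on study at once. That compares a monthly event count with a simultaneous headcount. The right comparison is with the 10 to 17 people passing through in a month. Against that figure the trigger is very high but not impossible, and it becomes more reachable at the pilot pace.

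Nor is a one-month window a separate fault merely because it exceeds one person's time on study. Events accumulate across participants, and the replacement proposed here also uses 30 days.

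Finally, nothing in the documents suggests an SAE rate of 5% or more, the products are marketed, and participants already smoke LCCs. This stands and limits the importance of the point.

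**Conclusion.** The point holds as a modest one about participant protection. At planned accrual, the written count would be met in about 1% of studies or fewer even with 12.5 SAEs among 125 participants, a level at odds with the plan's own expectation that SAEs will be rare. At the pilot pace the figure is about 1-5%. Study-level review therefore relies in practice on an unquantified pattern clause and on judgement at meetings. Both are real safeguards, but neither is a defined trigger. Item 4 also names no interim hold for enrolled participants.

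The result rests on accrual of 6.9 to 10 per month, 14 to 20 days on product, and assumed SAE rates that are a scan and not estimates. Dropout would shorten exposure and make the count harder still to reach. Harm is limited because individual SAEs are handled elsewhere in the plan. A hold would stop the study supplying a product but would not necessarily stop a participant smoking.

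**What to change.** Amend Appendix A, item 4 in two places.

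1. Replace the count with a reachable one, for example: *any SAE judged possibly or definitely related, or 3 or more SAEs of any cause in any 30 days, prompts review*. Keep the pattern clause. The exact count is for the investigators to choose.
2. Add to the determinations: *hold dispensing and crossover of the implicated product for enrolled participants until the determination is recorded*.

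The cost is wording in one item, using roles the plan already names. If 1-2% of participants have unrelated SAEs, the 3-in-30-days count would prompt an unneeded review in about 0.3-4% of studies at planned accrual, and somewhat more often if accrual is faster. A hold would affect the people then on study, on average 6.9 x 14/30.4 = 3.2 to 10 x 20/30.4 = 6.6. About a quarter of them (0.8 to 1.6) would be in Week 1 and due to cross into the implicated product. For those few, Visit 2 dispensing would be delayed, and the delay should be recorded with their randomized sequence.
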